8.4 Multiple Comparisons

No multiple comparison adjustment will be made in this study.

8.5 Methods for Handling Missing Data

For demographic and baseline characteristics, each variable will be analyzed using all available data. Patients with missing data will be excluded only from analyses for which data are not available.

8.6 Interim Analyses

There is no interim analysis planned in this study.

STATISTICAL ANALYSIS PLAN

Ivermectin Lotion 0.5%

Protocol / Study No. 71691702

9. TABLE, LISTING AND FIGURE SHELLS

The following shells are provided in order to provide a framework for the display of data from this study. These shells may not be reflective of every aspect of this study but are intended to show the general layout of the Tables, Listings and Figures that will be included in the final clinical study report. Tables, Listings and Figures are numbered following the ICH structure. Table headers, variables names and footnotes will be modified as needed following data analyses. All descriptive and inferential statistical analyses will be performed using SAS® statistical software Version 9.4 or higher, unless otherwise noted.

STATISTICAL ANALYSIS PLAN

Ivermectin Cream 0.5%

Protocol / Study No. 71691702

TABLE, LISTING AND FIGURE SHELLS

STATISTICAL ANALYSIS PLAN

Ivermectin Cream 0.5%

Protocol / Study No. 71691702

T16.1.9.1 Summary of Discontinued Patients

Patients	Test	Reference	Placebo	Total
Randomized	xxx	xxx	xxx	xxx
Completed Study	xxx	xxx	xxx	xxx
Terminated Early	xxx	xxx	xxx	xxx
Lost to Follow-Up	xxx	xxx	xxx	xxx
Withdrew Consent	xxx	xxx	xxx	xxx
Randomized in Error	xxx	xxx	xxx	xxx
etc.				

Test: Ivermectin Lotion, 0.5% (Actavis Laboratories UT, Inc.)

Reference: SKLICE® (ivermectin) Lotion, 0.5% (Arbor Pharmaceuticals, LLC)

Placebo: Placebo (vehicle) lotion (Actavis Laboratories UT, Inc.)

OUTPUT: L:\DEV\917\71691702\SAS\OUT\XXXX

Created on: ddmmmyy hh:mm

Page 1 of N

STATISTICAL ANALYSIS PLAN

Ivermectin Cream 0.5%

Protocol / Study No. 71691702

T16.1.9.2 Summary of Protocol Deviations

	Test	Reference	Placebo	Total
Total Patients with Protocol Deviations	xxx	xxx	xxx	xxx
Total Deviations	xxx	xxx	xxx	xxx
Outside Visit Window	xxx	xxx	xxx	xxx
Randomized in Error	xxx	xxx	xxx	xxx
Missed Visit	xxx	xxx	xxx	xxx
Restricted Medication	xxx	xxx	xxx	xxx
etc	xxx	xxx	xxx	xxx
Other	xxx	xxx	xxx	xxx

Test: Ivermectin Lotion, 0.5% (Actavis Laboratories UT, Inc.)

Reference: SKLICE® (ivermectin) Lotion, 0.5% (Arbor Pharmaceuticals, LLC)

Placebo: Placebo (vehicle) lotion (Actavis Laboratories UT, Inc.)

OUTPUT: L:\DEV\917\71691702\SAS\OUT\XXXX

Created on: ddmmmyy hh:mm

Page 1 of N

STATISTICAL ANALYSIS PLAN

Ivermectin Cream 0.5%

Protocol / Study No. 71691702

T16.1.9.3.1 Summary of Patients Excluded from Efficacy Analysis

STATISTICAL ANALYSIS PLAN

Ivermectin Cream 0.5%

Protocol / Study No. 71691702

		Test	Reference	Placebo	Total
Randomized	Total	xxx	xxx	xxx	xxx
Safety Population	Total	xxx	xxx	xxx	xxx
Excluded from Safety	Total	xxx	xxx	xxx	xxx
	Not randomized or did not receive study product	xxx	xxx	xxx	xxx
mITT Population	Total	xxx	xxx	xxx	xxx
Excluded from mITT	Total	xxx	xxx	xxx	xxx
	Did not dose	xxx	xxx	xxx	xxx
	etc.				
PP Population	Total	xxx	xxx	xxx	xxx
Excluded from Excluded from PPP	Total	xxx	xxx	xxx	xxx
	Restricted Medication	xxx	xxx	xxx	xxx
	etc.				

Test: Ivermectin Lotion, 0.5% (Actavis Laboratories UT, Inc.)

Reference: SKLICE® (ivermectin) Lotion, 0.5% (Arbor Pharmaceuticals, LLC)

Placebo: Placebo (vehicle) lotion (Actavis Laboratories UT, Inc.)

OUTPUT: L:\DEV\917\71691702\SAS\OUT\XXXX

Created on: ddmmmyy hh:mm

Page 1 of N

STATISTICAL ANALYSIS PLAN

Ivermectin Cream 0.5%

Protocol / Study No. 71691702

T16.1.9.3.2 Summary of Patients Included in Analysis Population by Study Center

Site No.	Name	Total Randomized	PP				mITT				Safety			
			Test	Reference	Placebo	Total	Test	Reference	Placebo	Total	Test	Reference	Placebo	Total
XXX	XXXX	XXX	XXX	XXX	XXX	XXX	XXX	XXX	XXX	XXX	XXX	XXX	XXX	XXX

Test: Ivermectin Lotion, 0.5% (Actavis Laboratories UT, Inc.)

Reference: SKLICE® (ivermectin) Lotion, 0.5% (Arbor Pharmaceuticals, LLC)

Placebo: Placebo (vehicle) lotion (Actavis Laboratories UT, Inc.)

OUTPUT: L:\DEV\917\71691702\SAS\OUT\XXXX

Created on: ddmmmyy hh:mm

Page 1 of N

STATISTICAL ANALYSIS PLAN

Ivermectin Cream 0.5%

Protocol / Study No. 71691702

T16.1.9.4 Summary of Demographic Data and Baseline Characteristics (Safety Population)

		Test (N = xxx)	Reference (N = xxx)	Placebo (N = xxx)	P-value
Age (years)	n	xxx	xxx	xxx	x.XXXX
	Mean ± SD	xx.x ± xx.x	xx.x ± xx.x	xx.x ± xx.x	
	Median	xx.x	xx.x	xx.x	
	Range	xx.x – xx.x	xx.x – xx.x	xx.x – xx.x	
Race	White	xxx (xx.x%)	xxx (xx.x%)	xxx (xx.x%)	x.XXXX
	Black/African American	xxx (xx.x%)	xxx (xx.x%)	xxx (xx.x%)	
	Native Hawaiian or other Pacific Islander	xxx (xx.x%)	xxx (xx.x%)	xxx (xx.x%)	
	Asian	xxx (xx.x%)	xxx (xx.x%)	xxx (xx.x%)	
	American Indian or Alaska Native	xxx (xx.x%)	xxx (xx.x%)	xxx (xx.x%)	
	Other	xxx (xx.x%)	xxx (xx.x%)	xxx (xx.x%)	
Gender	Female	xxx (xx.x%)	xxx (xx.x%)	xxx (xx.x%)	x.XXXX
	Male	xxx (xx.x%)	xxx (xx.x%)	xxx (xx.x%)	

N= number of patients in the specific treatment group; n= number of patient with data available; % is based on N

Test: Ivermectin Lotion, 0.5% (Actavis Laboratories UT, Inc.)

Reference: SKLICE® (ivermectin) Lotion, 0.5% (Arbor Pharmaceuticals, LLC)

Placebo: Placebo (vehicle) lotion (Actavis Laboratories UT, Inc.)

OUTPUT: L:\DEV\917\71691702\SAS\OUT\XXXX

Created on: ddmmmyy hh:mm

Page 1 of N

STATISTICAL ANALYSIS PLAN

Ivermectin Cream 0.5%

Protocol / Study No. 71691702

T16.1.9.4 Summary of Demographic Data and Baseline Characteristics (Safety Population)

		Test (N = xxx)	Reference (N = xxx)	Placebo (N = xxx)	P-value
Ethnicity	Hispanic or Latino	xxx (xx.x%)	xxx (xx.x%)	xxx (xx.x%)	x.XXXX
	Not Hispanic or Latino	xxx (xx.x%)	xxx (xx.x%)	xxx (xx.x%)	
Number of live lice	n	xxx	xxx	xxx	x.XXXX
	Mean ± SD	xx.x ± x.x	xx.x ± xx.x	xx.x ± xx.x	
	Median	xx.x	xx.x	xx.x	
	Range	xx.x – xx.x	xx.x – xx.x	xx.x – xx.x	

Note: N= number of patients in the specific treatment group; n= number of patient with data available; % is based on N

Test: Ivermectin Lotion, 0.5% (Actavis Laboratories UT, Inc.)

Reference: SKLICE® (ivermectin) Lotion, 0.5% (Arbor Pharmaceuticals, LLC)

Placebo: Placebo (vehicle) lotion (Actavis Laboratories UT, Inc.)

OUTPUT: L:\DEV\917\71691702\SAS\OUT\XXXX

Created on: ddmmmyy hh:mm

Page 1 of N

STATISTICAL ANALYSIS PLAN

Ivermectin Cream 0.5%

Protocol / Study No. 71691702

Similar tables will be created for T16.1.9.5 and T16.1.9.6

**T16.1.9.5 Summary of Demographic Data and Baseline Characteristics
(modified Intent-to-Treat Population)**

**T16.1.9.6 Summary of Demographic Data and Baseline Characteristics
(Per-Protocol Population)**

STATISTICAL ANALYSIS PLAN

Ivermectin Cream 0.5%

Protocol / Study No. 71691702

T16.1.9.7 Summary of Analysis Results of Primary Efficacy Endpoint (Proportion of Index Patients with Treatment Successes between Treatment Groups)

Equivalence: Per-Protocol Population

Treatment Group	Number of Patients (N)	Number of Treatment Successes (n)	Proportion of Treatment Successes (%)	Difference Between Treatments	
				Difference (%)	90% CI Evaluation
Test	xxx	xxx	xx.x		
Reference	xxx	xxx	xx.x	xx.x	xx.x – xx.x

Superiority: modified Intent-to-Treat Population

Treatment Group	Number of Patients (N)	Number of Treatment Successes (n)	Proportion of Treatment Successes (%)	P-value
Placebo	xxx	xxx	xx.x	
Test	xxx	xxx	xx.x	x.xxxx
Reference	xxx	xxx	xx.x	x.xxxx

Superiority of Active treatments over Placebo were tested using a two-sided Cochran-Mantel-Haenszel (CMH) test, stratified by clinical site, at the 5% significance level.

The superiority testing include patients in the mITT population using last observation carried forward (LOCF).

Test: Ivermectin Lotion, 0.5% (Actavis Laboratories UT, Inc.)

Reference: SKLICE® (ivermectin) Lotion, 0.5% (Arbor Pharmaceuticals, LLC)

Placebo: Placebo (vehicle) lotion (Actavis Laboratories UT, Inc.)

OUTPUT: L:\DEV\917\71691702\SAS\OUT\XXXX

Created on: ddmmmyy hh:mm

Page 1 of N

01/12/2017

■ Actavis LLC■

Page 29 of 52

STATISTICAL ANALYSIS PLAN

Ivermectin Cream 0.5%

Protocol / Study No. 71691702

T16.1.9.8 Summary of Analysis Results of Secondary Efficacy Endpoint (Proportion of All Randomized Patients with Treatment Successes between Treatment Groups)

Equivalence: Per-Protocol Population

Treatment Group	Number of Patients (N)	Number of Treatment Successes (n)	Proportion of Treatment Successes (%)	Difference Between Treatments	
				Difference (%)	90% CI Evaluation
Test	xxx	xxx	xx.x		
Reference	xxx	xxx	xx.x	xx.x	xx.x – xx.x

Superiority: modified Intent-to-Treat Population

Treatment Group	Number of Patients (N)	Number of Treatment Successes (n)	Proportion of Treatment Successes (%)	P-value
Placebo	xxx	xxx	xx.x	
Test	xxx	xxx	xx.x	x.XXXX
Reference	xxx	xxx	xx.x	x.XXXX

Superiority of Active treatments over Placebo were tested using a two-sided Cochran-Mantel-Haenszel(CMH) test, stratified by clinical site, at the 5% significance level.

Test: Ivermectin Lotion, 0.5% (Actavis Laboratories UT, Inc.)

Reference: SKLICE® (ivermectin) Lotion, 0.5% (Arbor Pharmaceuticals, LLC)

Placebo: Placebo (vehicle) lotion (Actavis Laboratories UT, Inc.)

OUTPUT: L:\DEV\917\71691702\SAS\OUT\XXXX

Created on: ddmmmyy hh:mm

Page 1 of N

01/12/2017

■ Actavis LLC■

Page 30 of 52

STATISTICAL ANALYSIS PLAN**Ivermectin Cream 0.5%****Protocol / Study No. 71691702****T16.1.9.9 Overall Summary of Adverse Events
(Safety Population)**

Description	Test	Reference	Placebo	Total
Patients Randomized	xxx	xxx	xxx	xxx
Patients with at least one AE	xx (xx.x%)	xx (xx.x%)	xx (xx.x%)	xx (xx.x%)
Discontinued study drug due to above AE	xx (xx.x%)	xx (xx.x%)	xx (xx.x%)	xx (xx.x%)
AEs reported	xxx	xxx	xxx	xxx
Mild	xx (xx.x%)	xx (xx.x%)	xx (xx.x%)	xx (xx.x%)
Moderate	xx (xx.x%)	xx (xx.x%)	xx (xx.x%)	xx (xx.x%)
Severe	xx (xx.x%)	xx (xx.x%)	xx (xx.x%)	xx (xx.x%)
Not Related	xx (xx.x%)	xx (xx.x%)	xx (xx.x%)	xx (xx.x%)
Related	xx (xx.x%)	xx (xx.x%)	xx (xx.x%)	xx (xx.x%)
Death	xx (xx.x%)	xx (xx.x%)	xx (xx.x%)	xx (xx.x%)
Serious AE	xx (xx.x%)	xx (xx.x%)	xx (xx.x%)	xx (xx.x%)

Test: Ivermectin Lotion, 0.5% (Actavis Laboratories UT, Inc.)

Reference: SKLICE® (ivermectin) Lotion, 0.5% (Arbor Pharmaceuticals, LLC)

Placebo: Placebo (vehicle) lotion (Actavis Laboratories UT, Inc.)

OUTPUT: L:\DEV\917\71691702\SAS\OUT\XXXX

Created on: ddmmmyy hh:mm

Page 1 of N

STATISTICAL ANALYSIS PLAN

Ivermectin Cream 0.5%

Protocol / Study No. 71691702

T16.1.9.10 Summary of Frequency of All Adverse Events by Body System (Safety Population)

Body System	MedDRA Term	Test (N = xxx)		Reference (N = xxx)		Placebo (N = xxx)		Fisher's P-value
		Events	Patients	Events	Patients	Events	Patients	
Patient with at least one AE	Total	xx	xx (xx.x%)	xx	xx (xx.x%)	xx	xx (xx.x%)	x.XXXX
Ear and labyrinth disorders	Ear pain	xx	xx (xx.x%)	xx	xx (xx.x%)	xx	xx (xx.x%)	x.XXXX
	etc.							
	etc.							

Comparison of treatment groups is with respect to the number of patients with at least one occurrence of the AE.

Test: Ivermectin Lotion, 0.5% (Actavis Laboratories UT, Inc.)

Reference: SKLICE® (ivermectin) Lotion, 0.5% (Arbor Pharmaceuticals, LLC)

Placebo: Placebo (vehicle) lotion (Actavis Laboratories UT, Inc.)

OUTPUT: L:\DEV\917\71691702\SAS\OUT\XXXX

Created on: ddmmmyy hh:mm

Page 1 of N

STATISTICAL ANALYSIS PLAN

Ivermectin Cream 0.5%

Protocol / Study No. 71691702

T16.1.9.11 Summary of Frequency of All Adverse Events by Severity (Safety Population)

Body System	MedDRA Term	Test			Reference			Placebo		
		# Events			# Events			# Events		
		(N=xx)			(N=xx)			(N=xx)		
Total AEs	Total AEs	xx(xx.x%)	xx(xx.x%)	xx (xx.x%)	xx(xx.x%)	xx(xx.x%)	xx (xx.x%)	xx (xx.x%)	xx (xx.x%)	xx (xx.x%)
Ear and labyrinth disorders	Ear pain	xx(xx.x%)	xx(xx.x%)	xx (xx.x%)	xx(xx.x%)	xx(xx.x%)	xx (xx.x%)	xx (xx.x%)	xx (xx.x%)	xx (xx.x%)
	Hypoacusis	xx(xx.x%)	xx(xx.x%)	xx (xx.x%)	xx(xx.x%)	xx(xx.x%)	xx (xx.x%)	xx (xx.x%)	xx (xx.x%)	xx (xx.x%)

etc.

N = Total number of events in each treatment group; Percentage is based on total number of events.

Test: Ivermectin Lotion, 0.5% (Actavis Laboratories UT, Inc.)

Reference: SKLICE® (ivermectin) Lotion, 0.5% (Arbor Pharmaceuticals, LLC)

Placebo: Placebo (vehicle) lotion (Actavis Laboratories UT, Inc.)

OUTPUT: L:\DEV\917\71691702\SAS\OUT\XXXX

Created on: ddmmmyy hh:mm

Page 1 of N

STATISTICAL ANALYSIS PLAN**Ivermectin Cream 0.5%****Protocol / Study No. 71691702****T16.1.9.12 Summary of Frequency of All Adverse Events by Relationship
(Safety Population)**

Body System	MedDRA Term	Test		Reference		Placebo	
		# Events		# Events		# Events	
		Related	Not Related	Related	Not Related	Related	Not Related
Total AEs	Total AEs	xx (xx.x%)	xx (xx.x%)	xx (xx.x%)	xx (xx.x%)	xx (xx.x%)	xx (xx.x%)
Ear and labyrinth disorders	Ear pain	xx (xx.x%)	xx (xx.x%)	xx (xx.x%)	xx (xx.x%)	xx (xx.x%)	xx (xx.x%)
	Hypoacusis	xx (xx.x%)	xx (xx.x%)	xx (xx.x%)	xx (xx.x%)	xx (xx.x%)	xx (xx.x%)
	etc.						

etc.

N = Total number of events in each treatment group; Percentage is based on total number of events.

Test: Ivermectin Lotion, 0.5% (Actavis Laboratories UT, Inc.)

Reference: SKLICE® (ivermectin) Lotion, 0.5% (Arbor Pharmaceuticals, LLC)

Placebo: Placebo (vehicle) lotion (Actavis Laboratories UT, Inc.)

OUTPUT: L:\DEV\917\71691702\SAS\OUT\XXXX

Created on: ddmmmyy hh:mm

Page 1 of N

STATISTICAL ANALYSIS PLAN

Ivermectin Cream 0.5%

Protocol / Study No. 71691702

T16.1.9.13 Summary of Frequency of Serious Adverse Events (Safety Population)

Body System	MedDRA Term	Test # Events	Reference # Events	Placebo # Events
Injury, poisoning and procedural complications	Alcohol poisoning	xx	xx	xx

Test: Ivermectin Lotion, 0.5% (Actavis Laboratories UT, Inc.)

Reference: SKLICE® (ivermectin) Lotion, 0.5% (Arbor Pharmaceuticals, LLC)

Placebo: Placebo (vehicle) lotion (Actavis Laboratories UT, Inc.)

OUTPUT: L:\DEV\917\71691702\SAS\OUT\XXXX

Created on: ddmmmyy hh:mm

Page 1 of N

STATISTICAL ANALYSIS PLAN

Ivermectin Cream 0.5%

Protocol / Study No. 71691702

T16.1.9.14 Summary of Frequency of Application Site Reaction (Safety Population)

Signs and Symptoms	Visit	Statistic	Placebo (N = xxx)	Test (N = xxx)	Reference (N = xx)
Edema	Visit 1	Absent	xxx (x.x%)	xxx (x.x%)	xxx (x.x%)
		Mild	xxx (x.x%)	xxx (x.x%)	xxx (x.x%)
		Moderate	xxx (x.x%)	xxx (x.x%)	xxx (x.x%)
		Severe	xxx (x.x%)	xxx (x.x%)	xxx (x.x%)
Visit 2					
Visit 3					
Visit 4					
Erythema					
Excoriation					
Pain					
Pruritus					
Pyoderma					

Test: Ivermectin Lotion, 0.5% (Actavis Laboratories UT, Inc.)

Reference: SKLICE® (ivermectin) Lotion, 0.5% (Arbor Pharmaceuticals, LLC)

Placebo: Placebo (vehicle) lotion (Actavis Laboratories UT, Inc.)

OUTPUT: L:\DEV\917\71691702\SAS\OUT\XXXX

Created on: ddmmmyy hh:mm

Page 1 of N

STATISTICAL ANALYSIS PLAN**Ivermectin Cream 0.5%****Protocol / Study No. 71691702****T16.1.9.15 Summary of Vital Signs
(Safety Population)**

Vital Signs	Visit	Statistic	Test (N = xxx)	Reference (N = xxx)	Placebo (N = xxx)
Systolic Blood Pressure (mmHg)	Visit 1	n	xxx	xxx	xxx
		Mean \pm SD	xxx.x \pm xxx.x	xxx.x \pm xxx.x	xxx.x \pm xxx.x
		Median	xxx.x	xxx.x	xxx.x
		Range	xxx.x – xxx.x	xxx.x – xxx.x	xxx.x – xxx.x
Visit 2					
Visit 3					
Visit 4					
Diastolic Blood Pressure (mmHg)					
Heart Rate (beats/min)					
Respiration Rate (breaths/min)					
Temperature (F)					

Test: Ivermectin Lotion, 0.5% (Actavis Laboratories UT, Inc.)

Reference: SKLICE® (ivermectin) Lotion, 0.5% (Arbor Pharmaceuticals, LLC)

Placebo: Placebo (vehicle) lotion (Actavis Laboratories UT, Inc.)

OUTPUT: L:\DEV\917\71691702\SAS\OUT\XXXX

Created on: ddmmmyy hh:mm

Page 1 of N

STATISTICAL ANALYSIS PLAN

Ivermectin Cream 0.5%

Protocol / Study No. 71691702

T16.1.9.16

(Safety Population)

Visit	Test (N = xxx)	Reference (N = xxx)	Placebo (N = xxx)
■■■	xxx (x.x%)	xxx (x.x%)	xxx (x.x%)
■■■	xxx (x.x%)	xxx (x.x%)	xxx (x.x%)

Test: Ivermectin Lotion, 0.5% (Actavis Laboratories UT, Inc.)

Reference: SKLICE® (ivermectin) Lotion, 0.5% (Arbor Pharmaceuticals, LLC)

Placebo: Placebo (vehicle) lotion (Actavis Laboratories UT, Inc.)

OUTPUT: L:\DEV\917\71691702\SAS\OUT\XXXX

Created on: ddmmmyy hh:mm

Page 1 of N

STATISTICAL ANALYSIS PLAN

Ivermectin Cream 0.5%

Protocol / Study No. 71691702

T16.1.9.17

(Safety Population)

Test (N = xxx)	Reference (N = xxx)	Placebo (N = xxx)
xxx (x.x%)	xxx (x.x%)	xxx (x.x%)

Test: Ivermectin Lotion, 0.5% (Actavis Laboratories UT, Inc.)

Reference: SKLICE® (ivermectin) Lotion, 0.5% (Arbor Pharmaceuticals, LLC)

Placebo: Placebo (vehicle) lotion (Actavis Laboratories UT, Inc.)

Re-infestation is defined as treatment success at Visit 2 and treatment failure at either Visit 3 or 4, or treatment success at Visits 2 and 3 and treatment failure at Visit 4.

OUTPUT: L:\DEV\917\71691702\SAS\OUT\XXXX

Created on: ddmmmyy hh:mm

Page 1 of N

STATISTICAL ANALYSIS PLAN

Ivermectin Cream 0.5%

Protocol / Study No. 71691702

L16.2.1 Listing of Discontinued Patients

Treatment Group	Patient Number	Discontinuation Reason	Population
Test	xxx-XXX-XX	Withdrew Consent	mITT
	xxx-XXX-XX	Lost to Follow-up	Safety

Reference

Placebo

Test: Ivermectin Lotion, 0.5% (Actavis Laboratories UT, Inc.)

Reference: SKLICE® (ivermectin) Lotion, 0.5% (Arbor Pharmaceuticals, LLC)

Placebo: Placebo (vehicle) lotion (Actavis Laboratories UT, Inc.)

OUTPUT: L:\DEV\917\71691702\SAS\OUT\XXXX

Created on: ddmmmyy hh:mm

Page 1 of N

STATISTICAL ANALYSIS PLAN

Ivermectin Cream 0.5%

Protocol / Study No. 71691702

L16.2.2 Listing of Protocol Deviations

Treatment Group	Patient Number	Protocol Deviation Summary	Population
Test	xxx-xxx-xx	Outside Visit Window	Safety

Reference

Placebo

Test: Ivermectin Lotion, 0.5% (Actavis Laboratories UT, Inc.)

Reference: SKLICE® (ivermectin) Lotion, 0.5% (Arbor Pharmaceuticals, LLC)

Placebo: Placebo (vehicle) lotion (Actavis Laboratories UT, Inc.)

OUTPUT: L:\DEV\917\71691702\SAS\OUT\XXXX

Created on: ddmmmyy hh:mm

Page 1 of N

STATISTICAL ANALYSIS PLAN

Ivermectin Cream 0.5%

Protocol / Study No. 71691702

L16.2.3.1 Listing of Patients Excluded from the Per-Protocol Population

Treatment Group	Patient Number	Exclusion Reason
Test	xxx-xxx-xx	Patient did not meet IE criterion.
	xxx-xxx-xx	Patient took prohibited medications

Reference

Placebo

Test: Ivermectin Lotion, 0.5% (Actavis Laboratories UT, Inc.)

Reference: SKLICE® (ivermectin) Lotion, 0.5% (Arbor Pharmaceuticals, LLC)

Placebo: Placebo (vehicle) lotion (Actavis Laboratories UT, Inc.)

OUTPUT: L:\DEV\917\71691702\SAS\OUT\XXXX

Created on: ddmmmyy hh:mm

Page 1 of N

STATISTICAL ANALYSIS PLAN

Ivermectin Cream 0.5%

Protocol / Study No. 71691702

L16.2.3.2 Listing of Patients Excluded from the Modified Intent-to-Treat Population

Treatment Group	Patient Number	Exclusion Reason
Test	XXX-XXX-XX	Patient did not have at least one post-randomization evaluation
	XXX-XXX-XX	Patient did not have at least one post-randomization evaluation

Reference

Placebo

Test: Ivermectin Lotion, 0.5% (Actavis Laboratories UT, Inc.)

Reference: SKLICE® (ivermectin) Lotion, 0.5% (Arbor Pharmaceuticals, LLC)

Placebo: Placebo (vehicle) lotion (Actavis Laboratories UT, Inc.)

OUTPUT: L:\DEV\917\71691702\SAS\OUT\XXXX

Created on: ddmmmyy hh:mm

Page 1 of N

STATISTICAL ANALYSIS PLAN

Ivermectin Cream 0.5%

Protocol / Study No. 71691702

L16.2.4.1 Listing of Demographic Data

Treatment Group	Patient Number	Age	Gender	Ethnicity	Race
Test	xxx-xxx-xx	30	Female	Not Hispanic or Latino	Black or African American

Reference

Placebo

Test: Ivermectin Lotion, 0.5% (Actavis Laboratories UT, Inc.)

Reference: SKLICE® (ivermectin) Lotion, 0.5% (Arbor Pharmaceuticals, LLC)

Placebo: Placebo (vehicle) lotion (Actavis Laboratories UT, Inc.)

OUTPUT: L:\DEV\917\71691702\SAS\OUT\XXXX

Created on: ddmmmyy hh:mm

Page 1 of N

STATISTICAL ANALYSIS PLAN

Ivermectin Cream 0.5%

Protocol / Study No. 71691702

L16.2.4.2 Listing of Medical History

Treatment Group	Patient Number	System	Diagnosis or Surgical Procedure	Start Date	End Date	Ongoing
Test	xxx-xxx-xx	Gynecologic	Menopause	2003	2003	

Reference

Placebo

Test: Ivermectin Lotion, 0.5% (Actavis Laboratories UT, Inc.)

Reference: SKLICE® (ivermectin) Lotion, 0.5% (Arbor Pharmaceuticals, LLC)

Placebo: Placebo (vehicle) lotion (Actavis Laboratories UT, Inc.)

OUTPUT: L:\DEV\917\71691702\SAS\OUT\XXXX

Created on: ddmmmyy hh:mm

Page 1 of N

STATISTICAL ANALYSIS PLAN

Ivermectin Cream 0.5%

Protocol / Study No. 71691702

L16.2.4.3 Listing of Concomitant Medications

Treatment Group	Patient Number	Medication	TX Area	Dosage	Frequency	Route	Start/End Date	Indication
Test	xxx-xxx-xx	LISINOPRIL	Yes	20 MG	QD	PO	yyyy-mm-dd/ yyyy-mm-dd	HYPERTENSION

Reference

Placebo

Test: Ivermectin Lotion, 0.5% (Actavis Laboratories UT, Inc.)

Reference: SKLICE® (ivermectin) Lotion, 0.5% (Arbor Pharmaceuticals, LLC)

Placebo: Placebo (vehicle) lotion (Actavis Laboratories UT, Inc.)

OUTPUT: L:\DEV\917\71691702\SAS\OUT\XXXX

Created on: ddmmmyy hh:mm

Page 1 of N

STATISTICAL ANALYSIS PLAN

Ivermectin Cream 0.5%

Protocol / Study No. 71691702

L16.2.5 Listing of Visit Date Information

Treatment Group	Patient Number	Informed Consent Date	Visit 1	Visit 2	Visit 3	Visit 4 or Discontinuation
Test	xxx-xxx-xx	yyyy-mm-dd	yyyy-mm-dd	yyyy-mm-dd	yyyy-mm-dd	yyyy-mm-dd

Test: Ivermectin Lotion, 0.5% (Actavis Laboratories UT, Inc.)

Reference: SKLICE® (ivermectin) Lotion, 0.5% (Arbor Pharmaceuticals, LLC)

Placebo: Placebo (vehicle) lotion (Actavis Laboratories UT, Inc.)

OUTPUT: L:\DEV\917\71691702\SAS\OUT\XXXX

Created on: ddmmmyy hh:mm

Page 1 of N

STATISTICAL ANALYSIS PLAN

Ivermectin Cream 0.5%

Protocol / Study No. 71691702

L16.2.6 Listing of Louse Examination Results

Treatment Group	Patient Number	Visit	Were Live Head Lice Present?	Number of Live Head Lice	Treatment Success	Duration of Louse Examination (minutes)
Test	xxx-xxx-xx	Visit 1	Yes	6		xx
		Visit 2	Yes	5		xx
		Visit 3	Yes	2		xx
		Visit 4	No	0	Yes	xx
	xxx-xxx-xx	Visit 1	Yes	6		xx
		Visit 2	Yes	5		xx
		Visit 3	Yes	2		xx
		Visit 4	Yes	2	No	xx
etc						

Reference

Placebo

Test: Ivermectin Lotion, 0.5% (Actavis Laboratories UT, Inc.)

Reference: SKLICE® (ivermectin) Lotion, 0.5% (Arbor Pharmaceuticals, LLC)

Placebo: Placebo (vehicle) lotion (Actavis Laboratories UT, Inc.)

OUTPUT: L:\DEV\917\71691702\SAS\OUT\XXXX

Created on: ddmmmyy hh:mm

Page 1 of N

STATISTICAL ANALYSIS PLAN

Ivermectin Cream 0.5%

Protocol / Study No. 71691702

L16.2.7.1 Listing of Adverse Events by Treatment Group

Treatment group	Patient Number	Body System/ MedDRA Term/ AE Term	TX Area	Start /End Date	Severity	Relationship to Study Drug	Outcome	Action Taken with Study Drug/ Other Action Taken	SAE?
Test	xxx-xxx-xx	Nervous system disorders/ headache/ Headache	No	yyyy-mm-dd / yyyy-mm-dd	Mild	Not Related	Recovered	Drug withdrawn/ None	No

Reference

Placebo

Test: Ivermectin Lotion, 0.5% (Actavis Laboratories UT, Inc.)

Reference: SKLICE® (ivermectin) Lotion, 0.5% (Arbor Pharmaceuticals, LLC)

Placebo: Placebo (vehicle) lotion (Actavis Laboratories UT, Inc.)

OUTPUT: L:\DEV\917\71691702\SAS\OUT\XXXX

Created on: ddmmmyy hh:mm

Page 1 of N

STATISTICAL ANALYSIS PLAN

Ivermectin Cream 0.5%

Protocol / Study No. 71691702

L16.2.7.2 Listing of Application Site Reactions

Treatment Group	Patient Number	Visit	Edema	Erythema	Excoriation	Pain	Pruritus	Pyoderma
Test	xxx-xxx-xx	Visit 1	0	0	0	1	0	0
		Visit 2	0	1	0	0	0	0
		Visit 3	0	0	0	1	0	0
		Visit 4	0	0	0	1	0	0

Reference

Placebo

Test: Ivermectin Lotion, 0.5% (Actavis Laboratories UT, Inc.)

Reference: SKLICE® (ivermectin) Lotion, 0.5% (Arbor Pharmaceuticals, LLC)

Placebo: Placebo (vehicle) lotion (Actavis Laboratories UT, Inc.)

OUTPUT: L:\DEV\917\71691702\SAS\OUT\XXXX

Created on: ddmmmyy hh:mm

Page 1 of N

STATISTICAL ANALYSIS PLAN

Ivermectin Cream 0.5%

Protocol / Study No. 71691702

L16.2.8.1 Listing of Pregnancy Test Results

Treatment Group	Patient Number	Visit 1	Visit 2	Visit 3	Visit 4 or Discontinuation
Test	xxx-xxx-xx	Negative	Negative	Negative	Negative

Reference

Placebo

Test: Ivermectin Lotion, 0.5% (Actavis Laboratories UT, Inc.)

Reference: SKLICE® (ivermectin) Lotion, 0.5% (Arbor Pharmaceuticals, LLC)

Placebo: Placebo (vehicle) lotion (Actavis Laboratories UT, Inc.)

OUTPUT: L:\DEV\917\71691702\SAS\OUT\XXXX

Created on: ddmmmyy hh:mm

Page 1 of N

STATISTICAL ANALYSIS PLAN

Ivermectin Cream 0.5%

Protocol / Study No. 71691702

L16.2.8.2 Listing of Vital Signs

Treatment Group	Patient Number	Visit	Systolic BP (mmHg)	Diastolic BP (mmHg)	Pulse Rate (beats/min)	Respiration Rate (breaths/min)	Temperature (F)
Test	xxx-xxx-xx	Visit 1	120	70	84	18	98.6
		Visit 2	140	80	74	18	97
		Visit 3	120	70	84	18	98.6
		Visit 4	140	80	74	18	97

Reference

Placebo

Test: Ivermectin Lotion, 0.5% (Actavis Laboratories UT, Inc.)

Reference: SKLICE® (ivermectin) Lotion, 0.5% (Arbor Pharmaceuticals, LLC)

Placebo: Placebo (vehicle) lotion (Actavis Laboratories UT, Inc.)

OUTPUT: L:\DEV\917\71691702\SAS\OUT\XXXX

Created on: ddmmmyy hh:mm

Page 1 of N

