5.0 SYNOPSIS

Protocol Number	71691702
Title	A Randomized, Double-Blind, Placebo-Controlled, Parallel-Design, Multiple-Site Clinical Study to Evaluate the Therapeutic Equivalence and Safety of Ivermectin Lotion 0.5% (Actavis Laboratories UT, Inc.) to SKLICE® (ivermectin) Lotion, 0.5% (Arbor Pharmaceuticals, LLC) in the Treatment of Human Head Lice Infestation
Objectives	
The objectives of this study are to:
 
1. Evaluate the therapeutic equivalence of the Test formulation, Ivermectin Lotion 0.5% (Actavis Laboratories UT, Inc.) to the Reference product, SKLICE® (ivermectin) Lotion, 0.5% (Arbor Pharmaceuticals, LLC) in the treatment of active head lice infestation.2. Demonstrate the superiority of the Test and Reference (active) treatments over Placebo treatment in patients with active head lice infestation.3. Compare the safety of Test, Reference and Placebo treatments in patients with active head lice infestation.
Sponsor	Actavis LLC
Study Products	
• Test: Ivermectin Lotion, 0.5% (Actavis Laboratories UT, Inc.)• Reference: SKLICE® (ivermectin) Lotion, 0.5% (Arbor Pharmaceuticals, LLC)• Placebo: Placebo (vehicle) lotion (Actavis Laboratories UT, Inc.) 
Study products will be supplied in 4 oz (117 g) tubes.

Dosage Regimen	Patients will be instructed to administer a single application of study product to the hair on Day 1.
Route of Administration	Topical
Treatment Randomization	[REDACTED]
Patient Population	Male and female patients, 6 months of age and older, with active Pediculus humanus capitis (human head lice) infestation, of which approximately 378 are expected to be index patients.
Study Design	Randomized, double-blind, placebo-controlled, parallel-design, multiple-site bioequivalence study with clinical endpoints
Study Conduct	Eligible patients will be randomized [REDACTED] to one of three treatments (Test, Reference or Placebo) at Visit 1. All members of the household will be examined for lice, [REDACTED]

CONFIDENTIAL PROTOCOL

A Randomized, Double-Blind, Placebo-Controlled, Parallel-Design, Multiple-Site Clinical Study to Evaluate the Therapeutic Equivalence and Safety of Ivermectin Lotion 0.5% (Actavis Laboratories UT, Inc.) to SKLICE® (ivermectin) Lotion, 0.5% (Arbor Pharmaceuticals, LLC) in the Treatment of Human Head Lice Infestation

Patients

will

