8.3.1 Adverse Events

All the adverse events (AEs) reported throughout the study will be coded and classified according to the MedDRA (Medical Dictionary for Regulatory Activities) coding dictionary (Version 20.0 or higher). Each adverse event is to be evaluated for date of start and end, seriousness, severity, causal relationship with the study drugs, action taken and outcome.

The total number and percentage of patients with at least one AEs, discontinued study drug due to AEs, AE severity and AEs related to investigational product, serious AEs and death will be summarized by treatment groups.

A summary table of the number and percent of patients with AEs by system organ class, preferred term, and treatment group will be presented. Each patient will be counted only once within each preferred term.

A frequency summary table of the number of AEs by system organ class, preferred term, severity, and treatment group will be presented. Severity will be classified as “Mild”, “Moderate”, or “Severe”.

Similarly, a frequency summary table of the number of AEs by system organ class, preferred term, and relationship to a study drug, and treatment group will be presented. Relationship to a study drug will be classified as “Related” or “Not Related”.

Adverse event frequencies will be compared between treatments using Fisher’s exact test. If the overall Fisher’s test is statistically significant, a pairwise test will be conducted for Test and Reference to determine if the difference in AEs is related to the active product.

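### The AE severity and relationship tables express each category as a share of the arm's own events, so no table clearly shows the proportion of patients with a severe or related AE

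*SAP*

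**What the plan says.** SAP 8.3.1 describes the severity table as a count of events: "A frequency summary table of the number of AEs by system organ class, preferred term, severity, and treatment group will be presented". It describes the relationship table the same way, in a sentence containing "a frequency summary table of the number of AEs by system organ class, preferred term, and relationship to a study drug, and treatment group will". The two shells in SAP section 9, T16.1.9.11 and T16.1.9.12, share one footnote on the denominator: "N = Total number of events in each treatment group; Percentage is based on total number of events".

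The serious-event shell, "T16.1.9.13 Summary of Frequency of Serious Adverse Events (Safety Population"), has one column of event counts per arm. It has no patient count, no percentage and no N.

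Two other shells give patient-level figures. T16.1.9.10 gives events, patients, patient percentages and a Fisher p-value by term, with the footnote "Comparison of treatment groups is with respect to the number of patients with at least one occurrence of the AE". It has no split by severity or relationship. T16.1.9.9 has an overall row for patients with any AE. Its severity and relationship rows come after the row "AEs reported xxx xxx xxx xxx", and the shell states no denominator. The text of 8.3.1 that appears to describe this table begins "The total number and percentage of patients with at least one AEs, discontinued study drug due to AEs, AE severity and AEs related to investigational" and goes on to serious AEs and death.

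**The concern.** Objective 3 is to compare safety across Test, Reference and Placebo. Protocol 11.8 asks for tables by treatment group that compare incidence, severity and relationship. The natural question is how many patients on each product had a severe AE, or one judged related.

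A percentage of an arm's own events does not answer that. The arm's AE burden is in the denominator, so a product that causes more AEs of every grade can show the same severity profile as one that causes few. One patient with several events can also fill a cell. At stake is how the safety comparison is read in the study report: a reader who goes by the percentages could see no difference, or one in the opposite direction, when more patients were in fact affected on one product.

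**Working it through.** The plan states no figure on this point, so there is none to reproduce. The check applies the shells' rule to hypothetical counts.

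**Inputs.** The denominator rule comes from the footnote to T16.1.9.11 and T16.1.9.12. Arm size is an assumption: the Protocol synopsis describes a population "of which approximately 378 are expected to be index patients", and 378 / 3 = 126 per arm if allocation is equal. The allocation ratio is redacted, so 2:2:1 and 3:3:1 are used as a range. All AE counts are invented.

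**Formulas.** Let *s* be severe events in an arm, *E* all events, *p* patients with at least one severe event, and *N* patients.
- The shell prints *s* / *E*.
- Patient incidence is *p* / *N*.
- The ratio of the printed percentages between arms 1 and 2 is (*s*1/*s*2) / (*E*1/*E*2). It is 1 when total events rise by the same factor as severe events, and below 1 when they rise by more.

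**Test against Reference, 126 per arm, 12 against 3 severe events (a factor of 4), each in a different patient:**

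| Total AEs | Shell percentage | Ratio of shell percentages | Patient percentage |
|---|---|---|---|
| 60 vs 15 (factor 4) | 12/60 = 20.0% vs 3/15 = 20.0% | 4/4 = 1 | 12/126 = 9.5% vs 3/126 = 2.4% |
| 80 vs 10 (factor 8) | 12/80 = 15.0% vs 3/10 = 30.0% | 4/8 = 0.5 | 9.5% vs 2.4% |
| 60 vs 60 (factor 1) | 12/60 = 20.0% vs 3/60 = 5.0% | 4/1 = 4 | 9.5% vs 2.4% |

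Fisher's exact test on the patient counts, 12/126 against 3/126, gives p = 0.030. The first row hides the difference, the second reverses it and the third shows it. Masking therefore needs total AEs to rise too.

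**Clustering.** Keep 12 of 60 against 3 of 15, but let the 12 severe Test events occur in 4 patients. The shell still prints 20.0% vs 20.0%. Patient incidence is 4/126 = 3.2% vs 3/126 = 2.4%, with Fisher p = 1.0. Neither the shell percentage nor the event count separates this case from the first row of the table.

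**Sensitivity to arm size.** For Test against Placebo with 12 and 3 affected patients:
- 2:2:1 (151:76) gives 12/151 = 7.9% vs 3/76 = 3.9%.
- 3:3:1 (162:54) gives 12/162 = 7.4% vs 3/54 = 5.6%.

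The Safety Population also includes non-index patients. Exclusion criterion 4 limits a household to three infested members, so an upper bound under equal allocation is 3 × 126 = 378 per arm. That gives 12/378 = 3.2% vs 3/378 = 0.8%. The SAP's own figure of about 364 index patients would change little: 364 / 3 is about 121 per arm, and 12/121 = 9.9% vs 3/121 = 2.5%. The shell percentages are the same in every case, because arm size does not enter them.

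**The case against.** The best defence is that the shells hide less than the footnote suggests, and much of it stands.

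- The event count is printed before each percentage, so in the first row of the table the reader sees 12 (20.0%) against 3 (20.0%). T16.1.9.11 also shows total events in its column header. Only the percentage misleads. The count is still not enough: it cannot separate one patient with repeated events from several patients, and it cannot be compared across arms of different size without a patient N, which none of the three shells gives.
- A rise in total AEs, which masking requires, would show in T16.1.9.10, where the Fisher p-values are on patients. The shells attach no test to T16.1.9.11 or T16.1.9.12.
- SAP 8.3.1 can fairly be read as promising patient numbers and percentages by severity and relatedness in T16.1.9.9. The row order in that shell points to events, and no denominator settles it. Even on the favourable reading, there would be no patient split by system organ class and preferred term.
- SAP section 9 lets headers and footnotes be modified. But 8.3.1 itself specifies event counts for the two tables, so a footnote change alone would not be enough.
- Listing L16.2.7.1 gives severity, relationship and seriousness for each AE by patient. That shows the data exist, but a listing is not a comparative summary.

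A reader might infer that T16.1.9.10 is the only place where patient incidence appears, or that the plan conceals any difference in AE burden. The documents support neither. T16.1.9.9 has a patient-level row for any AE, and overall burden is shown and tested by patient in T16.1.9.10.

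**Conclusion.** The concern holds as a limited reporting gap. T16.1.9.11 and T16.1.9.12 print percentages that cannot be read as risk to a patient, T16.1.9.13 has no patient count or denominator, and no shell clearly gives patient incidence by severity or relationship. Under the assumptions shown, a fourfold difference in affected patients can print as equal percentages or as half the other arm's percentage, but only when total AEs rise by at least the same factor.

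It would go too far to say that a true excess of severe or related AEs would disappear from the report. The distortion is confined to the percentage. It does not touch the event count, the overall patient incidence or the planned Fisher tests, and no equivalence or superiority conclusion depends on it. The sizes are illustrations: event counts are invented, arm sizes are assumed and the allocation ratio is redacted. That the percentage describes event mix rather than patients affected follows from the footnote and needs none of these assumptions. The change should be made because Objective 3 is a between-arm safety comparison, but it is not critical to the trial's main conclusions.

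**What to change.** - **SAP 8.3.1, T16.1.9.11 and T16.1.9.12:** add the number and percentage of patients with at least one AE in each category. Count each patient once, at worst severity or strongest relationship, within system organ class and preferred term. Use the arm's Safety Population N as denominator and show it in the column header. Keep event counts as a second column without percentages, and replace the footnote.
- **T16.1.9.13:** add patients n (%) on the same denominator beside the event count.
- **T16.1.9.9:** make the shell agree with 8.3.1 by labelling the severity, relationship, serious and death rows as patient-based and stating the denominator.

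The data are already collected by patient, as L16.2.7.1 shows. The cost is four shell edits, a few lines of SAP text, minor programming and slightly wider tables. Sample size, study conduct and the efficacy analyses are unaffected.
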